7.5 Instructions for Initiation of Each Cycle

To initiate treatment for Cycle 1 start, the following criteria must be met:

- WBC \leq 25,000/mm³ (leukapheresis and hydroxyurea are allowed to meet this criteria)
- Total bilirubin \leq 3x ULN
- Serum creatinine \leq 1.5x ULN
- The ANC is \geq 1000/mm³;
- The platelet count is \geq 50,000/mm³;
- Any grade II-IV drug-related non-hematological adverse effect that may have occurred has resolved to \leq grade 1 severity;
- Any other drug-related adverse events that may have occurred have resolved to grade \leq 2 severity;
- No evidence of life-threatening infection.

If these conditions are not met on Day 1 of a new cycle, the subject will be evaluated weekly and a new cycle of treatment will not be initiated until the toxicity has resolved as described above.

7.6 Ordering / How Supplied

Atezolizumab is investigational in this protocol and will be supplied by Genentech at no cost for use in this protocol.

7.7 Disposal and Destruction

Drug supply will be disposed of according to institutional standard operating procedures and policies. Accurate records of all investigational product received at and dispensed from the study site should be recorded on the drug accountability record.

7.8 Concomitant Therapy

Concomitant therapy consists of any medication (e.g., prescription drugs, over-the-counter drugs, vaccines, herbal or homeopathic remedies, nutritional supplements) used by a patient in addition to protocol-mandated treatment from 7 days prior to initiation of study treatment to the treatment discontinuation visit. All such therapies recorded in the patient's medical records.

7.6.1 Permitted Therapy

Patients are permitted to use the following therapies during the study:

- Oral contraceptives
- Hormone-replacement therapy
- Prophylactic or therapeutic anticoagulation therapy (such as warfarin at a stable dose or low-molecular-weight heparin)
- Inactivated influenza vaccinations
- Megestrol acetate administered as an appetite stimulant
- Mineralocorticoids (e.g., fludrocortisone)
- Corticosteroids administered for COPD or asthma
- Low-dose corticosteroids administered for orthostatic hypotension or adrenocortical insufficiency

In general, investigators should manage a patient's care (including preexisting conditions) with supportive therapies other than those defined as cautionary or prohibited therapies as clinically indicated, per local standard practice. Patients who experience infusion-associated symptoms

may be treated symptomatically with acetaminophen, ibuprofen, diphenhydramine, and/or H₂-receptor antagonists (e.g., famotidine, cimetidine), or equivalent medications per local standard practice. Serious infusion-associated events manifested by dyspnea, hypotension, wheezing, bronchospasm, tachycardia, reduced oxygen saturation, or respiratory distress should be managed with supportive therapies as clinically indicated (e.g., supplemental oxygen and B₂-adrenergic agonists; see Section 15.9). Premedication with antihistamines, antipyretics, and/or analgesics may be administered for the second and subsequent atezolizumab infusions only, at the discretion of the investigator.

7.8.1 Cautionary Therapy for Atezolizumab-Treated Patients

7.8.1.1 Corticosteroids and Tumor Necrosis Factor- α Inhibitors

Systemic corticosteroids and TNF- α inhibitors may attenuate potential beneficial immunologic effects of treatment with atezolizumab. Therefore, in situations in which systemic corticosteroids or TNF- α inhibitors would be routinely administered, alternatives, including antihistamines, should be considered. If the alternatives are not feasible, systemic corticosteroids and TNF- α inhibitors may be administered at the discretion of the investigator.

Systemic corticosteroids are recommended, at the discretion of the investigator, for the treatment of specific adverse events when associated with atezolizumab therapy (refer to Section 15.9).

7.8.1.2 Herbal Therapies

Concomitant use of herbal therapies is not recommended because their pharmacokinetics, safety profiles, and potential drug-drug interactions are generally unknown.

7.8.2 Prohibited Therapy

Use of the following concomitant therapies is prohibited as described below:

- Concomitant therapy intended for the treatment of cancer, with the exception of the standard of care course with surgery followed by adjuvant radiation as outlined (including, but not limited to, chemotherapy, hormonal therapy, immunotherapy, radiotherapy, and herbal therapy), whether health authority-approved or experimental, is prohibited for various time periods prior to starting study treatment, depending on the agent (see Section 4.2, and during study treatment, until disease progression is documented and the patient has discontinued study treatment).
- Investigational therapy (other than protocol-mandated study treatment) is prohibited within 30 days prior to initiation of study treatment and during study treatment.
- Live, attenuated vaccines (e.g., FluMist[®]) are prohibited within 4 weeks prior to initiation of study treatment, during treatment with atezolizumab, and for 5 months after the last dose of atezolizumab.
- Systemic immunostimulatory agents (including, but not limited to, interferons and IL-2) are prohibited within 4 weeks or five drug elimination half-lives (whichever is longer) prior to initiation of study treatment and during study treatment because these agents could potentially increase the risk for autoimmune conditions when given in combination with atezolizumab.
- Systemic immunosuppressive medications (including, but not limited to, cyclophosphamide, azathioprine, methotrexate, and thalidomide) are prohibited during study treatment because these agents could potentially alter the efficacy and safety of atezolizumab. Corticosteroids are permitted per section 7.4 for management of irAEs.

8. TREATMENT COMPLIANCE

The investigators and clinical trial coordinators will ensure appropriate patient treatment compliance according to the proposed treatment and surveillance timelines.

Patients will be informed that they have the right to withdraw from the study at any time for any reason, without prejudice to their medical care.

Patients who wish to stop taking the study medication will have the opportunity to remain in the study for long-term follow-up. The study will continue to monitor these patients for safety and oncologic treatment.

The Investigator will make every reasonable effort to keep each patient in the study unless it is in the patient's best interests to discontinue participation. If a patient is removed from the study or declines further participation, all End of Treatment evaluations should be performed if the patient is willing and able to be assessed. A description of the reason(s) for withdrawal from the study must be recorded on the case report form (CRF). The Investigator should also ensure that all patients are followed up for survival status after the Final Visit.

Patients who discontinue following entry will have relevant information completed and recorded on the CRF. All patients who discontinue because of adverse events or clinically significant laboratory abnormalities should be followed up until they recover or stabilize, and the subsequent outcome will be recorded. If any patient should die during the trial or within 30 days of stopping study treatment, the Investigator will inform the IRB. The cause of death should be recorded in detail, within 24 hours, on a serious adverse event (SAE) form and reported to institutional, federal and any other appropriate committees and/or sponsors.

9. SAFETY PARAMETERS AND DEFINITIONS

Safety assessments will consist of monitoring and reporting adverse events and serious adverse events per protocol. This includes all events of death and any study-specific issue of concern.

9.1 Adverse Event Definition

Any patient enrolled in the trial who signed the consent form and received at least one dose of atezolizumab will be eligible for adverse event reporting. Only laboratory abnormalities that result in signs or symptoms that require intervention or follow up and are considered clinically significant should be recorded as AEs. All other AEs whether serious or non-serious will be entered into the institutional database from the time of first protocol intervention up until 30 days after the last dose of study drugs. The Principal Investigator or designee will be responsible for assigning attribution to the study treatment.

This includes the following:

- AEs not previously observed in the subject that emerge during the protocol-specified AE reporting period, including signs or symptoms associated with squamous cell carcinoma that were not present prior to the AE reporting period.
- Complications that occur as a result of protocol-mandated interventions (e.g., invasive procedures such as cardiac catheterizations)
- If applicable, AEs that occur prior to assignment of study treatment associated with medication washout, no treatment run-in, or other protocol-mandated intervention.
- Preexisting medical conditions (other than the condition being studied) judged by the

investigator to have worsened in severity or frequency or changed in character during the protocol-specified AE reporting period.

The descriptions and grading scales found in the revised NCI Common Terminology Criteria for Adverse Events (CTCAE) version 5.0 will be utilized for AE reporting. All appropriate treatment areas should have access to a copy of the CTCAE version 5.0. A copy of the CTCAE version 5.0 can be downloaded from the CTEP web site

http://ctep.cancer.gov/protocolDevelopment/electronic_applications/ctc.htm.

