2.2 Endpoints

Primary Endpoint

pCR

Secondary Endpoints

1) Oncologic response to therapy:

- a) MPR
- b) 2-year EFS

2) Imaging and biomarker assessment of response to therapy.

- d) FDG avidity of nodal disease sites as measured by PET
- e) ORR as measured by CT or MRI of the head and neck per iRECIST criteria
- f) Plasma exosome levels

3) Safety and Tolerability assessment:

- a) Toxicity (adverse events) determined by CTCAE v5

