Immune-mediated hepatitis has been associated with the administration of atezolizumab. Eligible patients must have adequate liver function, as manifested by measurements of total bilirubin and hepatic transaminases, and liver function will be monitored throughout study treatment. Management guidelines for hepatic events are provided in Table 4.

Patients with right upper-quadrant abdominal pain and/or unexplained nausea or vomiting should have liver function tests (LFTs) performed immediately and reviewed before administration of the next dose of study drug.

For patients with elevated LFTs, concurrent medication, viral hepatitis, and toxic or neoplastic etiologies should be considered and addressed, as appropriate.

Table 4. Management Guidelines for Hepatic Events

Event	Management
Hepatic event, Grade 1	
 Continue atezolizumab. Monitor LFTs until values resolve to within normal limits or to baseline values.
Hepatic event, Grade 2	
All events:
 
 Monitor LFTs more frequently until return to baseline values. 
Events of > 5 days' duration:

Event	Management
	
 Withhold atezolizumab for up to 12 weeks after event onset.^a Initiate treatment with corticosteroids equivalent to 1–2 mg/kg/day oral prednisone. If event resolves to Grade 1 or better, resume atezolizumab.^b If event does not resolve to Grade 1 or better while withholding atezolizumab, permanently discontinue atezolizumab and contact the sponsor.^c
Hepatic event, Grade 3 or 4	
 Permanently discontinue atezolizumab.^c Consider patient referral to gastrointestinal specialist for evaluation and liver biopsy to establish etiology of hepatic injury. Initiate treatment with corticosteroids equivalent to 1–2 mg/kg/day oral prednisone. If event does not improve within 48 hours after initiating corticosteroids, consider adding an immunosuppressive agent. 
If event resolves to Grade 1 or better, taper corticosteroids over ≥ 1 month.

LFT = liver function test.

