Amylase and/or lipase elevation, Grade 2	
Amylase and/or lipase $> 1.5\text{--}2.0 \times ULN$:
 
 Continue atezolizumab. Monitor amylase and lipase weekly. For prolonged elevation (e.g., > 3 weeks), consider treatment with corticosteroids equivalent to 10 mg/day oral prednisone. 
Asymptomatic with amylase and/or lipase $> 2.0\text{--}5.0 \times ULN$:
 
 Treat as a Grade 3 event.
Amylase and/or lipase elevation, Grade 3 or 4	
 Withhold atezolizumab for up to 12 weeks after event onset.^a Refer patient to GI specialist. Monitor amylase and lipase every other day. If no improvement, consider treatment with corticosteroids equivalent to 1–2 mg/kg/day oral prednisone. If event resolves to Grade 1 or better, resume atezolizumab.^b If event does not resolve to Grade 1 or better while withholding atezolizumab, permanently discontinue atezolizumab and contact the sponsor.^c For recurrent events, permanently discontinue atezolizumab and contact the sponsor.^c
Immune-mediated pancreatitis, Grade 2 or 3	
 Withhold atezolizumab for up to 12 weeks after event onset.^a Refer patient to GI specialist. Initiate treatment with corticosteroids equivalent to 1–2 mg/kg/day IV methylprednisolone and convert to 1–2 mg/kg/day oral prednisone or equivalent upon improvement. If event resolves to Grade 1 or better, resume atezolizumab.^b If event does not resolve to Grade 1 or better while withholding atezolizumab, permanently discontinue atezolizumab and contact the sponsor.^c

Event	Management
	
 For recurrent events, permanently discontinue atezolizumab and contact the sponsor.^c
Immune-mediated pancreatitis, Grade 4	
 Permanently discontinue atezolizumab.^c Refer patient to GI specialist. Initiate treatment with corticosteroids equivalent to 1–2 mg/kg/day IV methylprednisolone and convert to 1–2 mg/kg/day oral prednisone or equivalent upon improvement. If event does not improve within 48 hours after initiating corticosteroids, consider adding an immunosuppressive agent. If event resolves to Grade 1 or better, taper corticosteroids over \geq 1 month.

GI = gastrointestinal.

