9.3.1 Adverse Events of Special Interest

AESIs are a subset of Events to Monitor (EtMs) of scientific and medical concern specific to the atezolizumab, for which ongoing monitoring and rapid communication by the Investigator to the Genentech is required. Such an event might require further investigation in order to characterize and understand it. Depending on the nature of the event, rapid communication by the Sponsor-Investigator to other parties (e.g., Regulatory Authorities) may also be warranted.

The following AEs are considered of special interest and must be reported to the Genentech Drug Safety expeditiously, irrespective of regulatory seriousness criteria:

- Cases of potential drug-induced liver injury that include an elevated ALT or AST in combination with either an elevated bilirubin or clinical jaundice, as defined by Hy's Law and based on the following observations:
 - Treatment-emergent ALT or AST $> 3 \times$ ULN (or $> 3 \times$ baseline value in disease states where LFTs may be elevated at baseline) in combination with total bilirubin $> 2 \times$ ULN (of which $\geq 35\%$ is direct bilirubin)
 - Treatment-emergent ALT or AST $> 3 \times$ ULN (or $> 3 \times$ baseline value in disease states where LFTs may be elevated at baseline) in combination with clinical jaundice
- Data related to a suspected transmission of an infectious agent by the study treatment, as defined below
 - Any organism, virus, or infectious particle (e.g., prion protein transmitting transmissible spongiform encephalopathy), pathogenic or non-pathogenic, is considered an infectious agent. A transmission of an infectious agent may be suspected from clinical symptoms or laboratory findings that indicate an infection in a patient exposed to a medicinal product. This term applies only when a contamination of study treatment is suspected.
- Systemic lupus erythematosus
- Events suggestive of hypersensitivity, infusion-related reactions, cytokine-release syndrome, macrophage activating syndrome, hemophagocytic lymphohistiocytosis
- Nephritis
- Ocular toxicities (e.g., uveitis, retinitis, optic neuritis)
- Grade ≥ 2 cardiac disorders (e.g., atrial fibrillation, myocarditis, pericarditis)
- Vasculitis
- Autoimmune hemolytic anemia
- Severe cutaneous reactions (e.g., Stevens-Johnson syndrome, dermatitis bullous, toxic epidermal necrolysis)
- Myelitis
- Facial paresis

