9.4.1 Adverse Event Reporting Period

The study period during which all AEs and SAEs must be reported beginning at initiation of study treatment until 30 days following the last administration of study treatment or study discontinuation/termination, whichever is earlier. After this period, investigators should only report SAEs that are attributed to prior study treatment.

Investigators will seek information on adverse events at each patient contact. All adverse events, whether reported by the patient or noted by study personnel, will be recorded in the patient's medical record.

Assessment of Adverse Events

All AEs and SAEs whether volunteered by the patient, discovered by study personnel during questioning, or detected through physical examination, laboratory test, or other means will be reported appropriately. Each reported AE or SAE will be described by its duration (i.e., start and end dates), regulatory seriousness criteria if applicable, suspected relationship to atezolizumab (see following guidance), and actions taken.

To ensure consistency of AE and SAE causality assessments, investigators should apply the following general guideline:

Yes

There is a plausible temporal relationship between the onset of the AE and administration of atezolizumab, and the AE cannot be readily explained by the subject's clinical state, intercurrent illness, or concomitant therapies; and/or the AE follows a known pattern of response to atezolizumab or with similar treatments; and/or the AE abates or resolves upon discontinuation of atezolizumab or dose reduction and, if applicable, reappears upon re-challenge.

No

Evidence exists that the AE has an etiology other than atezolizumab (e.g., preexisting medical condition, underlying disease, intercurrent illness, or concomitant medication); and/or the AE has no plausible temporal relationship to atezolizumab administration (e.g., cancer diagnosed 2 days after first dose of atezolizumab).

Expected adverse events are those adverse events that are listed or characterized in the Package Insert (P.I) or current Investigator Brochure (I.B).

Unexpected adverse events are those not listed in the P.I. or current I.B or not identified. This includes adverse events for which the specificity or severity is not consistent with the description in the P.I. or I.B. For example, under this definition, hepatic necrosis would be unexpected if the P.I. or I.B. only referred to elevated hepatic enzymes or hepatitis.

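### The symptom condition in Section 9.1 keeps asymptomatic laboratory toxicities that Section 7.4 acts on out of the AE-based safety counts, leaving them only as a Tier 3 grade shift

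*Combined protocol and SAP*

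**What the plan says.** The safety endpoint in Section 2.2 is "Toxicity (adverse events) determined by CTCAE v5". Section 9.1 decides which laboratory findings count towards it: "Only laboratory abnormalities that result in signs or symptoms that require intervention or follow up and are considered clinically significant" are to be entered as AEs. Signs or symptoms are a necessary condition. The sentence offers no alternative route for an abnormality that needs intervention without producing any.

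Other sections treat laboratory values differently.

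- **Section 7.4, Table 10.** The row for Grade 2 enzyme elevation has a line beginning "Asymptomatic with amylase and/or lipase" (above 2.0 and up to 5.0 x ULN) that is to be handled as Grade 3. The Grade 3 or 4 row reads "Withhold atezolizumab for up to 12 weeks after event onset". It adds possible corticosteroids, and permanent discontinuation if the elevation recurs or does not resolve. Pancreatitis has its own rows.
- **Section 7.4, Table 4.** For Grade 2 hepatic events the instruction is "Monitor LFTs more frequently until return to baseline values". A hold and corticosteroids follow if the event lasts more than 5 days, and Grade 3 or 4 brings permanent discontinuation. No symptom condition is stated.
- **Section 9.3.1.** The AEs of special interest (AESIs) include "Cases of potential drug-induced liver injury that include an elevated ALT or AST in combination with either an elevated bilirubin or clinical jaundice". One of the two qualifying patterns is purely numerical.
- **Section 9.4.1.** AEs and SAEs "detected through physical examination, laboratory test, or other means will be reported appropriately".
- **Section 10.1.** Under the toxicity endpoint, laboratory grade shift from baseline is a Tier 3 item. So are the broad proportions of patients with a drug-related AE, a Grade 3–5 AE, or discontinuation because of an AE.

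**The concern.** The protocol schedules blood tests to detect immune toxicity early and acts on the results. A patient who feels well can therefore have the drug held, be given corticosteroids or be taken off treatment because of a laboratory value. Under 9.1 as worded, that abnormality need not be recorded as an AE.

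Causality is assessed for AEs (9.1.1), and action taken and outcome are documented for AEs (9.3). An event that never becomes an AE has none of these attached. The AE-based proportions would then be biased downward, mainly for hepatic and pancreatic toxicity. These proportions are the safety summary most readers of a small single-arm trial will look at.

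**Working it through.** The plan states no figure on this point, so there is none to reproduce. The check traces cases through the text and then sizes the effect.

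**Step 1. Apply 9.1 to a patient without signs or symptoms.**

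- *Amylase or lipase above 2.0 and up to 5.0 x ULN (Table 10).* Asymptomatic by definition, so not an AE under 9.1, yet handled with a hold. It drops out of the drug-related count, and out of the discontinuation count if it recurs or fails to resolve. It does not affect the Grade 3–5 count: the line sits in the Grade 2 row, and handling it as Grade 3 is a management instruction, not a reporting grade.
- *Amylase or lipase elevation, Grade 3 or 4 (Table 10).* No symptom condition and separate from pancreatitis. If the patient has no symptoms it drops out of the same counts and also out of the Grade 3–5 count.
- *Liver-test elevation under Table 4 with no diagnosis recorded.* Grade 2 beyond 5 days brings a hold and corticosteroids; Grade 3 or 4 brings permanent discontinuation. The event drops out of the drug-related count. At Grade 3 or 4 it also drops out of the Grade 3–5 and discontinuation counts.
- *Hy's Law case met by ALT/AST and bilirubin values.* 9.3.1 calls it an AE and requires reporting; 9.1 does not admit it as an AE. The two sections contradict each other.

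**Step 2. See what remains.** Section 10.1 keeps the laboratory grade shift (Tier 3), which shows the value but not attribution or action. Section 8 follows patients who discontinue for AEs or for clinically significant laboratory abnormalities. By naming these as two reasons, it supports the reading that a laboratory-only stop need not be an AE.

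**Step 3. Size.** Inputs: N = 18 (Section 10.2); Tier 2 cut-offs of 10% for a specific AE and 5% for a specific Grade 3–5 AE or SAE (Section 10.1). The event rate q is not in the documents; 2% to 15% is assumed.

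One patient is 1/18 = 5.6%. The chance of at least one such patient is 1 − (1 − q)^18, and the expected number is 18q:

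- q = 2%: 1 − 0.98^18 = 30%; expected 0.36
- q = 5%: 1 − 0.95^18 = 60%; expected 0.9
- q = 10%: 1 − 0.90^18 = 85%; expected 1.8
- q = 15%: 1 − 0.85^18 = 95%; expected 2.7

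With exact 95% intervals, an unrecorded event is reported as 0/18 (0% to 18.5%). Recorded, one case is 5.6% (0.1% to 27.3%) and two are 11.1% (1.4% to 34.7%). One case of a specific Grade 3–5 term passes the 5% cut-off; two cases of a specific term of any grade pass the 10% cut-off.

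**The case against.** The best reply is that the plan has several other routes for these events.

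- **The toxicity endpoint.** A reader might infer that these toxicities are missing from it altogether. They are not: Section 10.1 reviews laboratory results alongside AEs and keeps the grade shift. This stands, and confines the point to the AE-based counts.
- **Diagnosis.** A reader might infer that a site would necessarily stop the drug and record nothing. Section 9.5.2.1 prefers a diagnosis to individual findings, so a hepatic case may well be entered as hepatitis. This stands for Table 4 whenever a diagnosis is made. It does not help with enzyme elevation in Table 10, which is listed apart from pancreatitis.
- **Discontinuations.** Sections 5.3 and 8 document the reason and follow the patient. This stands, but the event is still not an AE and holds are not covered.
- **Section 9.4.1.** It may only describe how AEs are detected, not which values qualify. A flat contradiction is therefore not shown; the fit with 9.1 is uneasy.
- **Thyroid events.** Table 6 is a tempting further example, but a weak one. A TSH below 0.1 mU/L leads only to considering a hold, the Grade 2–4 rows resume treatment once symptoms are controlled, and thyroid disorders are diagnoses in their own right.
- **Tiers.** Section 10.1 attaches no different analysis to Tier 2 and Tier 3, and membership needs a specific term, whereas the assumed rate pools several. A change of tier is a matter of presentation, not a changed conclusion.

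**Conclusion.** The point holds as a recording gap and an internal inconsistency. Read literally, 9.1 excludes asymptomatic laboratory toxicities that trigger action under 7.4 from the AE-based proportions in 10.1, and it contradicts 9.3.1 on Hy's Law cases. The case is clearest for Table 10, and good for Table 4 where no diagnosis is entered. The loss is of attribution and action taken, not of the laboratory value.

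Each unrecorded patient is 5.6 percentage points of 18. The 30% to 95% chance of at least one rests on an assumed rate of 2% to 15%. It is the chance that such an event occurs; it becomes the chance of a missed AE only if sites apply 9.1 literally and record no diagnosis. The denominator is planned accrual; Section 5.3 replaces patients who stop early, so the dosed group may be somewhat larger and each case slightly smaller. The primary pCR analysis is unaffected. The change is worth making because it is cheap and removes a downward bias from a stated safety endpoint.

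**What to change.** Amend the sentence in 9.1 so that a laboratory abnormality is recorded as an AE if it meets the present condition, **or** leads to a hold or discontinuation of atezolizumab or to treatment under Section 7.4, **or** meets an AESI definition in 9.3.1. Align 9.4.1 with the same sentence. A further criterion, CTCAE v5 Grade 3 or higher and clinically significant, is optional; the inconsistency does not require it.

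The cost is a short protocol amendment, a few more AE entries and slightly higher reported AE rates. The blood tests are already scheduled. The change concerns recording only, and no management rule in 7.4 is altered.
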